### **1.7.2 Dapagliflozin**

The safety profile of dapagliflozin has been evaluated in clinical development programs for T2DM, T1DM, heart failure and CKD. This includes more than 15,000 subjects treated with

dapagliflozin for T2DM, more than 1,000 subjects treated with dapagliflozin for T1DM, more than 1,400 subjects treated with dapagliflozin for DKD, and more than 2,000 subjects treated with dapagliflozin for heart failure. Overall, treatment with dapagliflozin 5 mg was similar to treatment with dapagliflozin 10 mg in both T1DM and T2DM. The safety profile of dapagliflozin was overall consistent across the studied indications.

The most commonly reported AEs associated with the use of dapagliflozin include genital infections, urinary tract infections, back pain, and polyuria. In addition, rash has been identified as an AE of unknown frequency in marketed use of dapagliflozin.

In the cardiovascular outcomes study, dapagliflozin on the Incidence of Cardiovascular Events (DECLARE), 8,574 patients received dapagliflozin 10 mg and 8,569 patients received placebo for a median exposure time of 48 months. Events of diabetic ketoacidosis (DKA) were reported in 27 patients in the dapagliflozin 10 mg group and 12 patients in the placebo group. The events occurred evenly distributed over the study period. Of the 27 patients with DKA events in the dapagliflozin group, 22 had concomitant insulin treatment at the time of the event.

The DAPA-CKD renal outcome study has shown 10 mg dapagliflozin to be efficacious and well tolerated in a wide range of patients with CKD (2152 patients treated with dapagliflozin; median follow-up = 2.4 years) (Heerspink et al, 2020a). In patients with an estimated glomerular filtration rate (eGFR) 25 to 75 mL/min/1.73m^2 dapagliflozin was shown to significantly reduce the combined risk of: 1) sustained decline in eGFR of at least 50%; 2) end-stage kidney disease; 3) or death from renal or cardiovascular causes (Heerspink et al, 2020a).

Taken together, SGLT2i have been shown to consistently reduce the risk of clinically important, patient-level cardiovascular outcomes and emerging data suggest that the combination of ACEi or ARB and SGLT2i should be routinely offered to patients with T2DM who have, or are at high risk of, progressive kidney disease (de Boer et al, 2020).

More detailed information about the known and expected benefits and potential risks of dapagliflozin may be found in the respective current IB (Edition 17).

### **1.7.3 Other Risks**

Given the distinct molecular mechanisms of action of MEDI3506 and dapagliflozin, no adverse drug-drug interaction is expected when both drugs are taken together.

For details on background information, risks and mitigations plans, and impact of COVID-19 on the current study, see Appendix F.

### 1.7.4 Overall Benefit/Risk Conclusion

Taking into account the measures taken to minimize risk to the subjects of this study, the potential risks identified in association with MEDI3506 and MEDI3506/dapagliflozin are justified by the anticipated benefits that may be afforded to subjects with DKD.

## 1.8 Research Hypotheses

### 1.8.1 Primary Hypothesis

MEDI3506 will reduce albuminuria compared with placebo on top of standard of care, including ACEi or ARB, and dapagliflozin.

### 1.8.2 Secondary Hypotheses

MEDI3506 will reduce albuminuria compared with placebo on top of standard of care, including ACEi or ARB, and will exhibit an acceptable safety, immunogenicity, and PK profile in subjects with DKD. Dapagliflozin on top of MEDI3506 will further reduce albuminuria.

## 2 OBJECTIVES AND ENDPOINTS

### 2.1 Primary Objective and Associated Endpoint

**Table 1 Primary Objective and Associated Endpoint**

Type	Objective	Endpoint
Efficacy	To evaluate the effect of MEDI3506 on albuminuria in subjects with DKD	Change from baseline to Day 169 (Week 24) in UACR compared to placebo. Central laboratory UACR results will be blinded to Investigators and Sponsor team starting from Visit 3 (Day 1) up to and including the EOS Visit.

DKD = Diabetic Kidney Disease; UACR = Urine albumin:creatinine ratio

### 2.2 Secondary Objectives and Associated Endpoints

**Table 2 Secondary Objectives and Associated Endpoints**

Type	Objective	Endpoint
Safety	To evaluate safety and tolerability of MEDI3506 with and without dapagliflozin in subjects with DKD	Measures of safety and tolerability including but not limited to: 
 
• Incidence of TEAEs and TESAEs
 
• Assessment of vital signs (SBP, DBP, heart rate, respiratory rate and body temperature)
 
• ECG
 
• LVEF as measured by echocardiogram
 

**Table 2 Secondary Objectives and Associated Endpoints**

Type	Objective	Endpoint
		
 
• BNP
 
• Laboratory assessments (hematology, clinical chemistry, and urinalysis)
 
• For subjects testing positive for COVID-19 during the intervention and follow-up periods, the number and proportion of subjects with AEs/SAEs, as well as the number and proportion of subjects with COVID-19 AEs/SAEs, and the proportion of asymptomatic subjects.
 

PK, Immunogenicity	To describe the PK and immunogenicity of MEDI3506 in subjects with DKD	MEDI3506 serum concentrations and ADA incidence occurring throughout the study
Efficacy	To evaluate the effect of MEDI3506 in combination with ACEi or ARB with and without dapagliflozin on albuminuria in subjects with DKD	
 
• Proportion of subjects with > 30% reduction in UACR at Day 169 (Week 24)
 
• Proportion of subjects with > 40% reduction in UACR at Day 169 (Week 24)
 
• Proportion of subjects with > 50% reduction in UACR at Day 169 (Week 24)
 
• Change from baseline to Day 85 (Week 12) in UACR
 
• Change from Day 85 (Week 12) to Day 169 (Week 24) in UACR
 

ACEi = angiotensin converting enzyme inhibitors; ADA = anti-drug antibody; AE(s) = adverse event(s); ARB = angiotensin receptor blockers; BNP = B-type natriuretic peptide; ECG = electrocardiogram; EOS = end of study; DBP = diastolic blood pressure; DKD = Diabetic Kidney Disease; LVEF = left ventricular ejection fraction; PK = pharmacokinetic; SAE(s) = serious adverse event(s); SBP = systolic blood pressure; TEAE(s) = treatment emergent adverse event(s); TESAE(s) = treatment emergent serious adverse event(s); UACR = urine albumin to creatinine ratio

CCI

CCI

CCI

### 3 STUDY DESIGN

#### 3.1 Description of the Study

##### 3.1.1 Overview

This is a Phase 2b, randomized, double-blind, placebo-controlled, multicenter study to evaluate the efficacy, safety, PK, and immunogenicity of MEDI3506 in adult subjects with DKD; defined as subjects with T2DM and an eGFR of 25-75 mL/min/1.73 m^2 with a urine albumin:creatinine ratio (UACR) in the range of 100-3000 mg/g, who meet all eligibility criteria. Furthermore, the additive effect of the SGLT2i dapagliflozin taken together with MEDI3506 on albuminuria will be assessed for 12 weeks when subjects will be treated with MEDI3506/placebo and dapagliflozin. Subjects who have started on the Phase 2a study prior to Amendment 2 will be transitioned to the Phase 2b and given dapagliflozin starting on Day 85 (Week 12). Subjects who have completed 12 weeks of treatment prior to implementation of Amendment 2 will continue on treatment with MEDI3506/placebo without dapagliflozin.

Approximately 565 subjects, from around 130 study sites among multiple countries will be randomized (95:95:95:140:140) to MEDI3506 30, 60, 120, or 300 mg, or volume-matched placebo. Note that the 19 subjects who were enrolled and discontinued prior to the study hold on 24 March 2020 due to COVID-19 are not included in the total count of 565 subjects.

[figure not shown]
Subjects will be dosed subcutaneously CCI

Following the signing of informed consent, subjects will be assessed for study eligibility during a screening period of up to 35 days (Day -37 to Day -3) followed by a 168-day (24-week) treatment period and a 70-day (10-week) follow-up period (Figure 1).

**Figure 1** Study Flow Diagram

ACEi = angiotensin converting enzyme inhibitor; ARB = angiotensin receptor blocker; eGFR = estimated glomerular filtration rate in mL/min/1.73m^2; Q4W = every 4 weeks; QD = once daily; T2DM = type 2 diabetes mellitus; UACR = urine albumin to creatinine ratio in mg/g.

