**Table 6 Schedule of Treatment Period Study Procedures**

Study Period	Treatment Period							Early D/c Visit
Visit Number	V3	V4	V5	V6	V7	V8	V9	
Procedure / Study Day	Day 1	Day 29 (± 5 days)	Day 57 (± 5 days)	Day 85 (± 5 days)	Day 113 (± 5 days)	Day 141 (± 5 days)	Day 169 (± 5 days)	

- a Including focused cardiac exam (Section 4.3.2.2).
- b For the first 2 doses of MEDI3506 or placebo, patients are to remain at the site for  $\geq 2$  hours or until stable, whichever is later. In addition, vital signs will be taken before and immediately after administration of MEDI3506 or placebo, and at 30 minutes ( $\pm 5$  minutes) as well as 120 minutes ( $\pm 10$  minutes) thereafter or until stable, whichever is later. Following the observation period, subject discharge will be at the discretion of the investigator. For all other dosing visits, vital signs will be collected 30 minutes ( $\pm 5$  minutes) after administration of MEDI3506 or placebo or when stable.
- c May be performed independently of other Visit 9 procedures within the visit window.
- d PK samples on MEDI3506/placebo dosing days will be collected pre-dose of MEDI3506/placebo administration.
- e Dapagliflozin PK samples will be collected at the following time points relative to dapagliflozin administration: Day 141 (predose and 2 h postdose) and Day 169 on study visit. Patients will be reminded to take dapagliflozin on site visits during dapagliflozin administration time (Day 85 to Day 168/Visit 6 to Visit 8).

- g If consent obtained.
- h After randomization. If, for any reason, the sample is not drawn pre-dose on Visit 3 (Day 1), it may be taken at any visit until the final follow-up visit/Early Discontinuation Visit.
- i Subjects collect 3 consecutive first morning void midstream urine samples (ideally day of visit and preceding 2 days [refrigerated overnight]) which are returned on the day of visit.
- j In the event that a dose cannot be administered within the window of the scheduled dosing date, the dose may be administered outside of the dosing window as long as it is at least 14 days prior to the next dose and recorded as a protocol deviation.
- k Subjects enrolled that have reached the Day 85 visit prior to Amendment 2 approval should continue in the study without the addition of dapagliflozin to their dosing regimen.

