### **4.8 Statistical Evaluation**

#### **4.8.1 General Considerations**

Tabular summaries will be presented by treatment group, with the 4 volume-matched placebo groups combined. Categorical data will be summarized by the number and percentage of

subjects in each category. Continuous variables will be summarized by descriptive statistics. Study populations are described in Table 11. Additional details of statistical analyses will be described in the statistical analysis plan (SAP).

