## 4.8.3 Efficacy

### 4.8.3.1 Primary Efficacy Analysis

The primary efficacy endpoint for this study is change from baseline to Day 169 (Week 24) in UACR compared to placebo and will be analyzed based on the Per Protocol Population. For the intercurrent events, if a subject is lost to follow-up, discontinues treatment due to AE or lack of efficacy, or uses prohibited medication, the UACR data are treated as missing after the event and no imputation is performed. As UACR is assumed to follow a log-normal

distribution, it will be log-transformed for statistical analysis purposes. The primary analysis will use a mixed model repeated measures (MMRM) analysis of change from baseline in UACR without multiplicity adjustment. The model will adjust for fixed categorical effects of treatment, visit, and treatment-by-visit interaction, randomization stratification factors, and the continuous covariates of baseline log UACR and baseline log UACR-by-visit interaction. UACR will be log-transformed before entering the data in the MMRM analysis to alleviate the skewness of the data. Randomization stratification factors are with SGLT2i background or not, in Japan or rest of world.

To allow generality for the covariance structure for the repeated measures, the variance-covariance matrix will be assumed to be unstructured ie, purely data dependent. If the unstructured variance-covariance matrix will not fit, then suitable alternatives will be considered with details provided in the SAP. In this MMRM model, all subjects and all data points will be included. No subjects will be excluded because of missing data, and no imputation will be done for missing data. Additionally, there will be no adjustment for multiplicity.

Additionally, the primary efficacy endpoint will also be analyzed using an analysis of covariance adjusting for treatment, randomization stratification factors, and baseline log UACR with last-observation-carried-forward (LOCF) imputation for missing postbaseline measurements.

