#### **4.8.3.2 Secondary Efficacy Analysis**

The change from baseline to Day 85 (Week 12) in UACR will be analyzed similarly to that of the primary efficacy endpoint based on the Full Analysis Population. Change from Day 85 (Week 12) to Day 169 (Week 24) in UACR will be analyzed similarly to that of the primary efficacy endpoint based on the Per Protocol Population. For the proportions of patients with > 30%, > 40%, and > 50% reduction in UACR, logistic regression models will be used adjusting for treatment, randomization stratification factors, and baseline albuminuria status based on the Full Analysis Population and the Per Protocol Population.

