  - (a) Section 3.1.1 (Overview), Section 3.1.2 (Treatment Regimen), Section 3.1.2 (Dose Rationale), Section 4.5.1.3 (Dose Preparation Steps), Section 4.6.1 (Methods for

- Assigning Treatment Groups), Section 4.8.2 (Sample Size): Additional MEDI3506 dose levels of 30 mg and 120 mg were added;
- (b) Section 3.1.1 (Overview), Section 4.1.1 (Number of Subjects), Section 4.8.2 (Sample Size): Number of study subjects was expanded to 565 total randomized subjects (505 evaluable subjects);
  - (c) Section 3.1.1 (Overview), Section 3.1.2 (Treatment Regimen), Section 3.2.1 (Dose Rationale), Section 4.6.1 (Methods for Assigning Treatment Groups), Section 4.8.1 (General Considerations): Two additional placebo groups were added in order to volume-match the newly added MEDI3506 dose groups and to maintain blinding;
  - (d) Section 3.1.1 (Overview): Number of study sites were increased to 150 among multiple countries;
  - (e) Section 3.1.1 (Overview), Section 3.1.2 (Treatment Regimen), Section 3.2.1 (Dose Rationale), Section 4.2.2 (Randomized Treatment Period): Dapagliflozin 10 mg daily was added to the treatment regimen for all patients from Day 85 to Day 168.
- 15 Section 3.1.1 (Overview), Section 4.2.2 (Randomized Treatment Period): Added a note that subjects that have reached the Day 85 visit prior to Amendment 2 approval should continue in the study without the addition of dapagliflozin to their dosing regimen.
- 16 Section 3.1.1 (Overview): Specified timing of the screening period for additional clarity.
- 17 CCI [REDACTED]

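### Pooled placebo may include subjects randomised before the 30 mg and 120 mg arms existed, and the efficacy models in the protocol have no term for randomisation period

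*Protocol*

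**What the plan says.** **Carry-over.** Protocol section 3.1.1, and again section 4.7.3, moves subjects who began under the Phase 2a design into Phase 2b: "Subjects who have started on the Phase 2a study prior to Amendment 2 will be transitioned to the Phase 2b and given dapagliflozin". Those who had already reached Day 85 follow a different rule. Under a footnote to Table 6 they "should continue in the study without the addition of dapagliflozin to their dosing regimen".

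**What was available before Amendment 2.** Item 14 of section 9.4 records that "Additional MEDI3506 dose levels of 30 mg and 120 mg were added" and that "Two additional placebo groups were added in order to volume-match the newly added MEDI3506 dose groups". By subtraction, earlier subjects could be assigned only to 60 mg, 300 mg or the matching placebos. The same amendment lowered the eGFR limit for entry from 30 to 25 mL/min/1.73 m². The log is used here as enrolment history, not as a conflict with the current text.

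**Comparator.** Section 4.8.1: "Tabular summaries will be presented by treatment group, with the 4 volume-matched placebo groups combined". Section 4.8.2 powers each dose against one placebo group of about 125 evaluable subjects.

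**Models.** Section 4.8.3.1 fixes the MMRM terms: "The model will adjust for fixed categorical effects of treatment, visit, and treatment-by-visit interaction, randomization stratification factors, and the continuous covariates". Those covariates are baseline log UACR and its interaction with visit. The stratification factors are SGLT2i background and Japan versus rest of world. The ANCOVA uses treatment, strata and baseline log UACR. The logistic models in section 4.8.3.2 use treatment, strata and "baseline albuminuria status based on the Full Analysis Population and the Per Protocol Population". None of these lists includes when the subject was randomised.

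**The concern.** A randomised comparison is protected when every control could have been assigned to the dose under test at the time of randomisation. A placebo subject randomised before Amendment 2 could not have been assigned to 30 mg or 120 mg, and entered under a narrower eGFR criterion. If outcomes differ between the two recruitment periods beyond what baseline UACR, SGLT2i background and region explain, the difference passes into the 30 mg and 120 mg contrasts. The 60 mg and 300 mg contrasts are less exposed, because those arms recruited in both periods. A bias that reaches two of four doses could disturb the dose ordering that a dose-ranging trial is meant to establish.

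A second route concerns Day 169. Subjects past Week 12 at Amendment 2 receive no dapagliflozin under the study regimen, and they can sit only in the 60 mg, 300 mg and placebo arms. In an analysis that keeps them, placebo would look worse relative to 30 mg and 120 mg if dapagliflozin lowers UACR, as the protocol's secondary hypothesis expects.

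**Working it through.** **1. The plan's own power.** Inputs from section 4.8.2: 30% reduction, so δ = ln(1/0.70) = 0.357; SD 1.0 on the log scale; one-sided α = 0.05; 85 evaluable for 30, 60 and 120 mg, 125 for 300 mg and for placebo. Power = Φ(δ/SE − 1.645).

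- 85 v 125: SE = √(1/85 + 1/125) = 0.1406; power 81.4% (stated 80%).
- 125 v 125: SE = √(2/125) = 0.1265; power 88.0% (stated at least 85%).

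The stated figures reproduce. The sample size is not in question.

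**2. Which analyses carried-over subjects enter.**

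| Status at Amendment 2 | Primary MMRM (Per Protocol) | Week 12 change (Full Analysis) | Day 169 responders |
|---|---|---|---|
| Not yet at Day 85, then given dapagliflozin | Yes | Yes | Both populations |
| Already past Week 12, no dapagliflozin | No | Yes | Full Analysis only |

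This follows from Table 11. The Per Protocol Population requires dapagliflozin after Week 12. The Full Analysis Population is everyone randomised and dosed.

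**3. Size of the bias on the log-UACR scale.** Let m be the number of carried-over placebo subjects among the 125 evaluable, and s the drift left after covariate adjustment. Neither is in the protocol; both are assumed below. Bias in the 30 mg and 120 mg contrasts = (m/125) × s. One-sided type I error = 1 − Φ(1.645 − bias/0.1406). With s = 0.2:

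| m | Share of placebo | Bias (log units) | Type I error, drift raises placebo change | Type I error, opposite drift |
|---|---|---|---|---|
| 0 | 0% | 0 | 5.0% | 5.0% |
| 5 | 4% | 0.008 | 5.6% | 4.4% |
| 10 | 8% | 0.016 | 6.3% | 3.9% |
| 20 | 16% | 0.032 | 7.8% | 3.1% |

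In the unfavourable direction, m = 20 is a spurious effect of about 3% (e^0.032 = 1.033). Halving the drift to 0.1 halves each bias: m = 10 then gives 5.6%.

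**4. Full Analysis responders at Day 169.** These are proportions in a logistic model, so the formula in step 3 does not apply. If k of about 140 placebo subjects never had dapagliflozin and each has a responder probability lower by d, the placebo proportion falls by (k/140) × d. Neither k nor d is given. The direction favours 30 mg and 120 mg if dapagliflozin lowers UACR. Size depends on k, and d would differ for subjects already taking another SGLT2 inhibitor.

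**5. Power if 30 mg and 120 mg are compared with concurrent placebo only.** Placebo n = 125 − m, same formula as step 1: m = 0, 81.4%; m = 5, 80.8%; m = 10, 80.2%; m = 20, 78.8%.

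**The case against.** The strongest objection is that there may be nobody to whom this applies. The only early subjects that the protocol counts are 19 who entered and stopped before the March 2020 hold, and section 3.1.1 leaves them out of the 565. Appendix F, added by Amendment 2, still speaks of enrolment resuming. The transition rule shows that provision was made, not that it was used. This stands: a reader might infer that pooled placebo does contain non-concurrent controls, and the protocol does not support that as fact. It does not rule it out either. The rule is still in the current text, and Table 11 does not bar the 19 from the Full Analysis Population if they were randomised and dosed.

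Second, the drift is assumed and has no known sign, and it must survive adjustment for baseline UACR and strata. This stands too. Inflation is one of two possibilities.

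Third, the Per Protocol definition already keeps subjects without dapagliflozin out of the primary analysis, and the responder analyses are run on that population as well. That is correct, so a reader should not infer that they distort the primary result. It does not protect the Full Analysis responder analysis. Nor does it deal with carried-over subjects who did receive dapagliflozin, since they qualify for the primary MMRM.

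Fourth, the SAP is not shown, and section 4.8.3.5 allows further sensitivity analyses. One cannot infer that no adjustment exists anywhere. The claim is only that the model terms fixed in the protocol omit the period.

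**Conclusion.** The point holds conditionally. If the plan is followed as written and any placebo subject carried over from before Amendment 2, the 30 mg and 120 mg doses are compared partly with non-concurrent placebo in the primary MMRM or the Full Analysis analyses, with no adjustment for period.

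The likely size is modest. For 5 to 20 carried-over evaluable placebo subjects and a drift of 0.2 log units, type I error for these two doses is about 5.6% to 7.8% in one direction and 4.4% to 3.1% in the other. At a count of zero there is no effect. The count and the drift are both assumptions.

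For the Full Analysis Day 169 responder analysis the direction is known, given a dapagliflozin effect, but the size is not. A reader might carry the type I error figures above across to it; they describe a difference in log means, not a logistic comparison of proportions, and should not be used there.

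**What to change.** - State how many subjects randomised before Amendment 2 are in each analysis set, by arm, and whether any of the 19 pre-hold subjects are in the Full Analysis Population. If the count is zero, one sentence closes the matter.
- If it is not zero, add randomisation period (before/after Amendment 2) as a fixed effect to the MMRM, ANCOVA and logistic models. In the MMRM include period-by-visit, so that the Day 169 contrast is adjusted for drift at Day 169.
- As a sensitivity analysis, compare 30 mg and 120 mg only with placebo subjects randomised after Amendment 2.
- Exclude from the Full Analysis Day 169 responder analysis those who by calendar date were never scheduled for dapagliflozin. The rule depends on date alone, not on outcome or treatment received.
- Fix all of this before unblinding.

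**Cost.** One degree of freedom in the ANCOVA and logistic models, a few more in the MMRM, and a small loss of precision in the 30 mg and 120 mg contrasts. The concurrent-placebo comparison has about 80.2% power with 10 carried-over placebo subjects and 78.8% with 20, against 81.4% with none, so it should support the primary comparison and not replace it.
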